Unique to this setting is the potential to identify high risk pharmaceutical opioid users, a population that is difficult to locate and engage. Interventions using brief behavior change counseling (BBCC) have been shown to significantly improve health behaviors such as alcohol use and injury, to increase entry into drug treatment as well as to reduce costs. Evidence is promising, but limited, regarding the impact of BBCC on opioid related risk behaviors.

This prospective, multi-site, randomized trial will study the effectiveness of an intervention that combines OOPEN with BBCC for both heroin users (n=500) and pharmaceutical opioid users at elevated risk for overdose (n=500). The primary outcome is subsequent opioid overdoses, ascertained by follow up interviews conducted at 3, 6 and 12 months as well as via administrative records for up to 24 months (i.e. medical records, ambulance responses, and death certificates). Hypotheses to be investigated include that the intervention recipients will have: 1) lower rates of opioid overdose, 2) reduced drug use and overdose risk behaviors, 3) more appropriate health care utilization, and 4) lower total health care costs. We will also explore whether the intervention impacts HIV risk behaviors.

Introduction

This research proposes the first prospective, clinical trial to test the effectiveness of an intervention to prevent opioid overdoses among pharmaceutical opioid users and heroin users. Naloxone distribution programs for heroin users are widespread and descriptive studies have been conducted, but prospective, randomized studies necessary to prove effectiveness have not been conducted. To date no research has been published on how to prevent overdoses among pharmaceutical opioid users, now the largest group represented in fatal drug overdoses nationally. The intervention combines two widely used interventions for related health behaviors that have not previously been combined: 1) opioid overdose prevention, education and intervention with naloxone (OOPEN) for heroin users, and 2) brief behavior change counseling (BBCC) which has been shown to prevent future harms for a range of substances.

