 - Enrolled in opioid substitution program (e.g. methadone or suboxone) and receiving doses.

Inclusion for heroin users:

- 2) Use of heroin through any route of administration at least 2 times in the last 30 days (or if institutionalized recently, in the most recent month they were not institutionalized) with or without other risks being present.

Inclusion for prescription-type opioid users:

- 3) Use of pharmaceutical opioids at least 2 times in the last 30 days (or if institutionalized recently, in the most recent month they were not institutionalized) with other risks being present.

Inclusion for opiate registry users:

- 4) Average daily dose of prescribed opioids consumed is 30 mg morphine equivalent analgesic dose or higher without other risks being present.

In the case of known pregnancy, subjects will not be excluded and will be offered naloxone if randomized to the intervention arm.

Exclusion criteria

- 1) Unwilling to allow further access to medical or drug treatment records.
- 2) Inability to communicate in English.
- 3) Current active suicidal ideation.
- 4) Significant cognitive or psychiatric impairment (per judgment of clinical staff)
- 5) Inability to provide adequate contact information to assist with follow-up.
- 6) Under age 18 or over age 70 at time of recruitment.
- 7) Not currently living in Washington State or planning to move from Washington State within the following year.

8) Receiving treatment for sexual assault.

9) Have non-expired take-home naloxone at home, on their person, or in their possessions.

Participation in the study is not appropriate for subjects under care for terminal illness, as known reduced life expectancy may skew study results, and the use of high doses of opioid medications may be used during end of life care.

Potential Subjects Identified

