Secondary data on health care and drug treatment utilization will be obtained from Washington State (separate IRB action pending) using the following sources:

- Treatment and Assessment Report Generation Tool (*TARGET*) for drug treatment admissions data
- The Comprehensive Hospital Abstract Reporting System (CHARS) for hospital admissions

Information on any ambulance transports will be obtained from the Seattle Fire Department's Medic 1 unit.

In the event of a subject death during the study we will request information on cause of death from the King County Medical Examiner's Office. If a subject cannot be located we will also check this source to see if they have died and if so to obtain data on the cause of death. If we are unable to locate a subject during the course of the study or at final follow-up we will utilize the King County Jail Inmate Look-up Service. At no time will subjects be contacted or study procedures attempted while the subject is incarcerated.

Intervention Description

Standard care for patients who have used opioids would vary according to individual clinical need and might include referral to drug treatment or detoxification services. Standard care would not include OOPEN and BBCC interventions as specified in this grant. After baseline data are obtained subjects assigned to the intervention undergo the following procedures:

A brief behavior change counseling (BBCC) session

- Conveys subjects' risk for overdose, based on the baseline measures
- Engages them in a reflective discussion of the pros and cons of their current patterns of use
- Has the patients identify behavior change(s) they are interested in making to improve their health
- Encourages them to share opioid overdose prevention and intervention information and materials with their family, friends, housemates, and/or drug using partners.

Education and training on opioid overdose prevention and intervention with naloxone (OOPEN)

- Subjects will view a training video on study laptops that reviews:
 - Information on risk factors for overdose and how to prevent and reduce the risk of overdose

- How to recognize an opioid overdose
- The importance of calling 911
- How to intervene in an overdose
 - Positioning a victim in rescue position
 - Brief overview of rescue breathing
 - Training on how and when to administer naloxone

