Aim 1 Test whether the intervention group has lower rates of opioid overdose and longer time to occurrence of overdose. Overdose will be ascertained at 12 months via self-report and across at least 24 months via administrative data. Because randomized controlled studies are designed to account for potential confounding factors by distributing confounders, measured and unmeasured, equally across comparison and intervention groups, the initial unadjusted analysis will be a logistic regression analysis comparing the probability of opioid overdose in the two study arms. To examine differences in the time to overdose and to account for time varying covariates, such as overdose risk factors, survival analyses will be conducted with the outcome time to overdose(s). A Cox proportional hazards model will be used to investigate the possible association between these factors and event time. We will use sandwich standard error estimates in all statistical tests. Multivariable logistic regression analyses will be conducted to examine the association between predictors and moderators and of the odds of overdose occurrence. Predictors will include treatment assignment and overdose risk factors such as concomitant drug use, interruption in tolerance and homelessness. Potential effect modification will be assessed by including interaction terms for the treatment assignment by severity of opioid and other substance use as measured by the ASSIST. For the pharmaceutical opioid only group, effect modification by opioid user type will be assessed; opioid user typologies will be based upon which inclusion criteria subjects met.

Aim 2 Test whether the intervention group has fewer overdose risk behaviors. These are measured as both binary and continuous data. Binary data will be examined with logistic

regression and continuous data analyzed with ordinary least-squares regression. Analyses will adjust for the overdose risk behavior level or frequency reported at baseline as a concomitant variable, the outcome is the overdose risk behavior at 12 months, and the primary predictor is the treatment group assignment. We will compute robust standard error estimates for each model and use them in all hypothesis tests and confidence intervals.

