Aims 3 and 4 Test whether the intervention group has more appropriate health care utilization and lower total health care costs. We will analyze utilization for three separate outcomes: ED visits, outpatient visits, and inpatient hospital admissions as we would expect the intervention to result in declines in ED and inpatient care with concomitant increases in outpatient care over time as patients stabilize their health status. For these analyses we will use a rate modeling approach (negative binomial or Poisson regression, with an exposure adjustment should there be a need to account for differing amounts of follow-up time). We will examine health care costs (combined hospital and ambulance costs) from the health care system perspective.

Mean-per-month health care costs will be calculated for both pre- and post-randomization periods for each individual. We will assess the difference in health care costs across the two study arms by regressing post-randomization mean health care costs on study arm, and controlling for pre-randomization mean health care costs (which should reduce variance and increase power) along with other important covariates. We expect that 500 per arm will be an adequate number to support the use of Ordinary Least-Squares (OLS) regression to model mean cost differences, but will use Generalized Linear Models (GLM) models to examine the sensitivity of OLS results. In addition, we will calculate unadjusted and adjusted cost offsets by adding the cost of the intervention to health care costs and comparing average monthly total costs of services for the intervention group to the average for the standard care group.

Aim 5 Test whether the intervention group has fewer HIV risk behaviors. These are measured as both binary and continuous data. Binary data will be examined with logistic regression and continuous data analyzed with ordinary least-squares regression.

Other analyses

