In order to determine whether there is recruitment reactivity, whether those enrolled in either arm of the study have a change in behaviors compared to those not enrolled, we will examine ED re-visit rates at two years for those receiving standard care compared to those with similar demographic characteristics, CPT codes and ED visit dates, but were not enrolled. While this will not directly measure the impact of recruitment on overdose, it will provide some information about recruitment reactivity. Subsequent to intent to treat analyses we will examine whether any subjects in the standard care group received take-home naloxone and overdose prevention and intervention training i.e. “crossed over”. If so, it is possible that this intermediate group might be more similar to the intervention than the standard care group. Crossovers will be identified by an interview question, such as “Did you possess or have ready access to naloxone during the past 3/6 months?” If there is a group that crossed over, post-hoc analyses will compare overdose rates at two years for the cross over group compared to each of the other two study arms. Completion level of administrative data will be assessed by the interview questions at each follow up that document what types of services, in broad categories, were

obtained at non-HMC or non-UWMC facilities or ambulance services not in Seattle-King County. This will allow for an evaluation of *ascertainment bias*, that is, how complete data based on HMC/UWMC and King County ambulance data are and whether there are differential levels of data completion by study arm assignment.

Missing data and dropouts

Missing data will be minimized by the study procedures described above. However, missing data are inevitable and could lead to biased results. Baseline data values and study arm assignment will be examined to determine the relationship with missingness. Sensitivity analyses will be conducted that assume any person lost to follow up had constant levels of drug use based upon their most recent measurement point. This will provide some guidance as to the amount of bias possibly introduced by missing data.

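### Ambulance data come from Seattle only, but the completeness check assumes King County coverage, so county runs outside Seattle are absent and its ambulance part does not count them as absent

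*Combined protocol and SAP*

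**What the plan says.** All references are to the combined protocol and SAP.

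- **Source.** Secondary Data Sources: "Information on any ambulance transports will be obtained from the Seattle Fire" Department's Medic 1 unit. No other section names a second ambulance source.
- **Check.** Other analyses says that completeness of the administrative data will be judged from follow-up interview questions about services "obtained at non-HMC or non-UWMC facilities or ambulance services not in Seattle-King County". The purpose is to learn "how complete data based on HMC/UWMC and King County ambulance data are", and whether completeness differs by arm.
- **Who can be enrolled.** The exclusion criteria remove only people "Not currently living in Washington State or planning to move from Washington State within the following year". Residence in Seattle is not required.
- **Use of the data.** The opening summary lists as sources for the primary outcome the follow-up interviews and "administrative records for up to 24 months (i.e. medical records, ambulance responses, and death certificates"). The schedule of measures lists ambulance use under Aim 3. Planned analyses states for Aim 4: "We will examine health care costs (combined hospital and ambulance costs) from the health care system perspective".
- **Timing.** Planned analyses, Aim 1: "Overdose will be ascertained at 12 months via self-report and across at least 24 months via administrative data". Interviews take place at 3, 6 and 12 months.

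**The concern.** The check is the plan's own safeguard against incomplete administrative data. It can work only if the services it asks about are exactly those that the data do not hold. Here the data are described by city and the check by county, so one area falls between the two. Ambulance runs there are not in the data, and the ambulance part of the check treats the area as covered.

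At stake are the ambulance counts, the ambulance component of cost, and the completeness figure that readers would use to judge ascertainment. Ambulance responses are also one of several sources for overdose, so some primary-outcome events could be affected. Completeness by arm matters because the intervention teaches subjects to call 911, so ambulance contact could plausibly differ between arms. For this area, the ambulance part of the check could not show whether it does.

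**Working it through.** The point rests on comparing two sections, not on a calculation.

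**Step 1: coverage by place.** Assumption: the Seattle Fire Department's data cover the city only. The documents do not state the unit's service area.

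| Place of ambulance run | In the named ambulance source? | Asked about by the ambulance part of the check? |
|---|---|---|
| Seattle | Yes | No (not needed) |
| King County outside Seattle | No | No |
| Outside King County | No | Yes |

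The middle row is the gap. Statewide eligibility means that runs there can occur.

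**Step 2: what else could record such a run.**

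- *Ends at HMC or UWMC:* the hospital record can show the overdose. The ambulance run and its cost are still missing.
- *Ends in admission elsewhere:* CHARS, listed for hospital admissions, can show it. The facility part of the check can also flag it, up to 12 months.
- *Ends in another emergency department without admission:* no named administrative source holds it. The facility part of the check and self-report can pick it up to 12 months.
- *Attended but not transported:* no named administrative source holds it. Self-report can pick up the overdose to 12 months.
- *Fatal:* the death data can show it.

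In every row the ambulance record is lost. The overdose itself is lost only if all the other sources miss it. Background and Rationale says that nearly all Seattle overdoses in which medics gave naloxone go to the HMC emergency department, so those events tend to have a second record. The documents give no such statement for the rest of the county.

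**Step 3: timing.** After the 12-month interview there is neither self-report nor any interview on which to run the check. For heroin users the sample size rests on a one-year rate, a period that self-report covers. For pharmaceutical opioid users it rests on a two-year rate, so their second year is where the gap bears most on Aim 1.

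**Step 4: the plan's sample size, for scale only.** The inputs from Sample Size Calculation are 20% versus 10%, power 0.80 and level 0.05. Sidedness is not stated; a two-sided test is assumed.

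- Without continuity correction: n0 = [1.96 × √(2 × 0.15 × 0.85) + 0.8416 × √(0.16 + 0.09)]² / 0.10² = (0.9897 + 0.4208)² / 0.01 ≈ 199.
- With continuity correction: n = (n0/4) × [1 + √(1 + 4/(n0 × 0.10))]² ≈ 218.5, rounded up to 219. This matches the plan, and the figure is not in dispute.

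Now suppose that a fraction of overdoses is lost equally in both arms, from any cause. The fractions are assumed.

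| Fraction lost | Observed rates | n per arm (corrected) | Power at 250 per arm (corrected) |
|---|---|---|---|
| 0 | 20% v 10% | 219 | 0.855 |
| 10% | 18% v 9% | 247 | 0.805 |
| 20% | 16% v 8% | 283 | 0.745 |

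This shows how sensitive power is to total under-capture, before any loss to follow-up. It does not estimate what this gap contributes.

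**The case against.** The strongest reply is that the check is wider than its ambulance part. It also asks about facilities other than HMC and UWMC, so a run ending at another hospital may be flagged as an outside-facility service. Overdose is not ascertained by ambulance data alone. The reply is right on both counts, and it limits the point to the ambulance record and to overdoses that no other source holds.

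A second reply is that a county-wide source may have been intended, so that Secondary Data Sources is merely incomplete. That is possible. The interview form is not in the documents either, and Other analyses only summarises its questions. But the two sections still disagree, and a data request that follows the first would leave the check misaligned.

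A third reply is that ambulance runs are not among the three utilisation outcomes modelled under Aim 3, which are emergency department visits, outpatient visits and admissions. This is correct. The Aim 3 effect is on the ambulance measure in the schedule, while ambulance cost does enter the Aim 4 analysis.

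A reader might infer more than the documents support:

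- *That a fixed share of overdoses is lost.* A missing ambulance record is not a missing overdose, and the documents give neither the share of runs outside the city nor the share of overdoses attended by ambulance.
- *That the comparison between arms is biased.* The 911 training makes a difference in ambulance contact plausible, but nothing in the documents shows differential loss.

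**Conclusion.** The point holds in a limited form. As written, the named source covers Seattle, the check assumes King County, and ambulance runs in the rest of the county are neither held nor counted as absent by the ambulance part of the check. Ambulance use and ambulance costs would be under-counted, and the completeness of the ambulance data overstated. For overdose, the exposure is limited to events recorded nowhere else, mainly in months 12 to 24 and chiefly relevant to the pharmaceutical opioid stratum.

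The size of the loss, and whether it differs by arm, cannot be determined from the documents. The conclusion assumes that Medic 1 data stop at the city boundary and that the interview questions follow the summary in Other analyses. It is worth correcting because it affects a stated safeguard and is cheap to put right.

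**What to change.** Make Secondary Data Sources and Other analyses agree on which ambulance data are obtained, in one of two ways:

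1. **Obtain county-wide ambulance data** and name the source or sources in Secondary Data Sources. The check then fits the data as it stands. This is the only option that also covers months 12 to 24. It costs one wider data request.
2. **Keep the Seattle source and reword the follow-up item** to ask about any ambulance service other than Seattle Fire Medic 1, or any ambulance use outside the city of Seattle. It costs one reworded item. It depends on subjects recalling the service or the place after an overdose, and it helps only through the 12-month interview. It measures the gap but does not fill it.

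Under either option, compute completeness by arm against the source actually obtained. Under the second, report ambulance counts and costs as covering Seattle runs only, and say that ambulance completeness after 12 months is not assessed.

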- 2) Overdose Risk Assessment: This assessment is used to determine the potential for future overdose based on prior overdose history, current drug use practices and social context for current drug use. This assessment is not standardized but is compiled from individual items of known risk factors for overdose.
- 3) World Health Organization Quality of Life (WHOQOL-BREF). This is a short assessment to measure general health and physical, social and emotional functioning.
- 4) World Health Organization Alcohol, Smoking and Substance Involvement Screening Test (WHO-ASSIST v.3). This is a multi-item tool to determine areas of substance use and misuse. This assessment battery screens for recent and lifetime use of a variety of substances, including illicit drugs, alcohol, pharmaceuticals and tobacco products.
- 5) Age of First Use: Subjects are asked to provide the ages they first used a variety of substances.
- 6) HIV Risk Assessment Battery: This assessment is used to determine the potential for contracting HIV, hepatitis and other blood-borne illnesses based on drug use and sexual use behaviors.
- 7) Overdose History: This assessment will collect information related to any prior overdose that the subject has experienced or witnessed.
- 8) EQ-5D-3L: This validated quality of life measure asks about problems in mobility, self-care, usual activities, pain and discomfort, anxiety and depression and overall health.

Locator information:

Subjects will be asked to provide a number of sources to ensure they can be contacted for 3, 6 and 12 month follow-up visits. However, because we anticipate a number of high risk subjects to be indigent, subjects may be enrolled if they provide at least one primary source of locator information.

Randomization

Subjects will be randomized to receive either standard of care or the study intervention. We will recruit equal numbers of subjects in the intervention and control arms of the study, meeting eligibility criteria as heroin user or primarily pharmaceutical opioid users.

Follow-up Visits

Follow-up visits will occur at 3, 6 and 12-month after enrollment. All interviews will be by phone. Most assessments given at the baseline interview will be repeated at each follow-up

point. In addition to the assessments subjects will be asked questions about whether they have naloxone and, if not, what happened to any naloxone that was given to them.

Secondary Data Sources

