- Subjects will be given a study brochure that covers the information in the video and reviews the Washington State 911 Good Samaritan overdose law which provides immunity from prosecution for drug possession charges to overdose victims and bystanders who seek aid in an overdose event.
- Prescribing and dispensing overdose rescue kits including 2 doses of intra-nasal naloxone, a disposable rescue breathing mask, and disposable gloves.
- Subjects in the intervention group will be informed that they may have one replacement of the naloxone kit (2 doses) during the 12 month study period.

We expect the intervention to take 30-45 minutes on average based on our experience and that this is feasible and reasonable for subjects and interventionists.

Fidelity assessment for the BBCC will be done with the shortened Motivational Interviewing Treatment Integrity (MITI) instrument.

Schedule of and Sources Data Obtainment

MEASURES	DATA SOURCES AND TIMING					
	Interview			Administrative		
	Case Report Form	Base-line	3 & 6 mos.	12 mo.	Up to 10 yrs.	Up to 10 yrs.
PRIMARY AIMS						
Aim 1: Overdose						
Subject overdosed prior 3/6* months	X		X			
Subject overdosed Y/N & Date						X
Aim 2: Drug use and other overdose risk behaviors						
Alcohol/Drugs 3/6 month use frequency	X		X		X	
Opioid use following interruption past 3/6 months	X		X		X	
Using opioids without others present	X		X		X	
Avg. daily opioid dose- Prescribed Opioid Users	X		X		X	
Opioid substitution drug treatment prior 3/6	X		X		X	
Other drug treatment sought or used prior 3/6	X		X		X	
SECONDARY AIMS						
Aim 3: Health care utilization						

ED, Outpatient, Inpatient and Ambulance- # & Aim 4: Health care costs Hospital-based total direct health care costs			x	x
Aim 5: HIV Risk Behaviors	x	x	x	x
CO-VARIATES & POTENTIAL EFFECT MODIFIERS				
Demographics	x			
Employment, health insurance, income, housing	x	x	x	
Alcohol/Drugs ages of first use	x			
Medical status and satisfaction (WHO QOL BREF, EQ-5D- 3L)	x	x	x	
Behavior change plans and readiness	x			
Overdose lifetime history	x			
Possessed, "carried" naloxone, # of days past 3/6	x	x	x	
Overdose # witnessed events past 3/6 months	x	x	x	
Source of naloxone- Study, other	x	x	x	
Subject had naloxone administered to them, #, by Disposition of naloxone	x	x	x	x
Subject had negative/allergic reaction to naloxone	x	x	x	
FIDELITY ASSESSMENT OF BASELINE				
Overdose prevention & intervention training. Item Motivational Interviewing Treatment Integrity 3.1.1	x			

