*Past 3 months timeline for 3 and 6 month follow ups, past 6 months used at 12 month follow up.

Brief Behavioral Change Counseling (BBCC)

The BBCC will be conducted according to the demeanor and guidelines of Motivational Interviewing (MI), a style for counseling patients about sensitive behaviors and for giving them information to enhance their health and safety in a non-judgmental manner. MI has been widely implemented in brief intervention studies for drug use and other behavior change. MI is non-confrontational and respectful of subjects' autonomy to discuss or not discuss sensitive topics. The BBCC will consist of 4 elements:

- 1) The interventionist will show to the patient an approximately 8-minute video on overdose prevention, recognition and intervention, which subjects will view on a laptop while they are using headphones. The interventionist will debrief the video with subjects and answer questions.
- 2) Next, the interventionist will review with subjects their overdose risk. This task involves informing subjects of the “good news” about overdose risks they are NOT incurring in their current behaviors for the purpose of reinforcing and hopefully continuing more positive health behaviors (e.g., not inappropriately mixing other drugs or alcohol with

opiates). Next, the interventionist will respectfully and in a neutral tone review with subjects the behaviors that currently place them at risk for opiate overdose (e.g., using opiates when alone or after a long period of abstinence).

- 3) From the video and risk feedback, the interventionist will segue into an open discussion of any changes subjects are thinking of making to increase their safety from overdosing. If at any time during the interview, subjects indicate that they would prefer to quit opiates or to seek opiate detox or treatment, the interventionist will help with these referrals. The discussion will culminate in a summary of healthy changes, if any, that subjects intend to make. Subjects will take with them a handout that has been customized to summarize any changes subjects indicate that they want to make.

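### Overdose recognition is taught in one arm only and the protocol gives no operational definition of a self-reported overdose, so the arms may not share a reporting threshold after randomization

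*Combined protocol and SAP*

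**What the plan says.** **Training.** The Intervention Description lists "How to recognize an opioid overdose" among the video topics, and a brochure repeats the video's content. The Brief Behavioral Change Counseling section describes an "approximately 8-minute video on overdose prevention, recognition and intervention", which the interventionist debriefs before reviewing the subject's own overdose risk. The counseling also "Encourages them to share opioid overdose prevention and intervention information and materials with their family, friends, housemates, and/or drug using partners". All of this follows the baseline assessment.

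**Control arm.** "Standard care would not include OOPEN and BBCC interventions as specified in this grant".

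**Outcome.** Under Planned analyses, Aim 1: "Overdose will be ascertained at 12 months via self-report and across at least 24 months via administrative data". The data schedule lists the Aim 1 interview item as "Subject overdosed prior 3/6* months". Of the Overdose History instrument, Baseline Assessments says: "This assessment will collect information related to any prior overdose that the subject has experienced or witnessed". No section defines overdose by its signs, says that a definition is read to subjects, provides for adjudication, or states how self-report and records are combined.

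**Checks.** The ascertainment-bias check under Other analyses concerns care obtained outside the covered hospitals and ambulance services, and "whether there are differential levels of data completion by study arm assignment". The sensitivity analysis under Missing data and dropouts concerns drug use. Follow-up is by telephone, and masking of interviewers is not mentioned.

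**The concern.** Part of the intervention teaches the construct that the primary outcome asks about. Between the baseline and follow-up interviews, one arm is told what an overdose looks like and the other is not. If that changes what a subject is prepared to call an overdose, the same physiological event can be counted in one arm and missed in the other. Companions matter too. They may be the ones who tell a subject what happened while he or she was unconscious, and only intervention subjects are encouraged to inform them.

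An error of this kind differs by arm, so a larger sample does not remove it. It sits in the respondent, so masking interviewers would not remove it either. Baseline overdose history is taken before the training and cannot calibrate a later change. What is at stake is the Aim 1 comparison: a real benefit could be hidden, or a difference could appear where none exists.

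**Working it through.** **Inputs from Sample Size Calculation:** 20% versus 10%, power 0.80, 0.05 level, 219 needed per arm and 250 enrolled per arm, separately for each opioid user type. The powered comparison covers one year for heroin users and two years for pharmaceutical opioid users.

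**Assumed inputs, not in the documents:** a 30% relative change in trained-arm reporting, and the share *s* of events known only from self-report (1 or 0.5). The remaining events are taken to be caught by records equally in both arms.

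**Step 1: the plan's own figure.** Let p̄ = (0.20 + 0.10)/2 = 0.15. The two-sided two-proportion formula gives

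n₀ = [1.960 √(2 × 0.15 × 0.85) + 0.842 √(0.16 + 0.09)]² / 0.10² = 199 per arm.

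With the continuity correction, n = (n₀/4)[1 + √(1 + 4/(0.10 n₀))]² = 219. This matches the plan, and the sample size is not in dispute.

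**Step 2: power with a shared threshold, 250 per arm.**

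Power = Φ{[|p₁ − p₂| − 1.960 √(2p̄(1 − p̄)/250)] / √([p₁(1 − p₁) + p₂(1 − p₂)]/250)}, without continuity correction.

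For 20% versus 10%: Φ[(0.10 − 1.960 × 0.03194)/0.03162] = 0.88.

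**Step 3: trained arm reports 30% more.** Observed trained-arm risk = true risk × (1 + 0.30*s*).

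| True risks (control, trained) | s | Observed, trained arm | Chance of a significant difference |
|---|---|---|---|
| 20%, 10% | 1 | 10% × 1.30 = 13% | 0.56 |
| 20%, 10% | 0.5 | 10% × 1.15 = 11.5% | 0.74 |
| 20%, 20% | 1 | 20% × 1.30 = 26% | 0.36 |
| 20%, 20% | 0.5 | 20% × 1.15 = 23% | 0.13 |

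In the last two rows the significant difference runs against the intervention.

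**Step 4: the opposite direction.** Suppose the trained arm reports 30% less and the true risk is 20% in both arms. With s = 1 the observed risks are 20% and 20% × 0.70 = 14%, and the same formula gives a 0.43 chance of a significant difference, now falsely favoring the intervention. With s = 0.5 they are 20% and 20% × 0.85 = 17%, and the chance is 0.14.

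**Step 5: unequal against merely incomplete reporting.** With true risks of 20% and 10%, suppose both arms report 80% of events: 16% versus 8%, risk ratio 0.50, power 0.79. If only controls report 80%: 16% versus 10%, risk ratio 0.63, power 0.51. Most of the loss comes from the difference between arms.

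**The case against.** **The form is not in the documents.** The schedule entry is shorthand, and the question as asked is not shown. Most baseline assessments are repeated at follow-up, so event detail may be collected. This stands: the protocol states no definition, but it does not follow that the form has none.

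**Direction.** A reader might infer that training must raise reporting and so hide a benefit. The documents do not support that. The training also covers rescue breathing and naloxone, which are responses to severe events, and could narrow the term so that heavy sedation no longer counts. Counseled subjects who know their arm may also under-report.

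**Population.** A reader might expect the worst effect in pharmaceutical opioid users, for whom the word may be less familiar. Yet their comparison is powered on two years and self-report ends at 12 months, so it leans more on records. Self-report weighs most in the one-year heroin comparison. There the term is not new: in the local survey cited under Background and Rationale, 16% of heroin users reported their own overdose in the prior year and 41% had witnessed one.

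**Records.** Medical, ambulance and death records do not use the subject's label, so the all-self-report figures are an upper-end illustration. This also stands. But the plan gives no rule for combining the sources and no records-only analysis, and an overdose reversed at home may leave no record. Records are not wholly neutral either, because only one arm is taught the importance of calling 911.

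**Conclusion.** The concern holds as a risk that is cheap to reduce. The documents establish three things: recognition training in one arm only, no stated operational definition of overdose, and no check on self-report by arm. From these it follows that the arms may not share a reporting threshold. That they do not share one, or that the trained arm reports more, would be inference beyond the documents.

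For an assumed 30% rise in trained-arm reporting, power falls from 0.88 to between 0.56 and 0.74, and the chance of a significant difference under no effect is between 13% and 36%, as the self-reported share runs from all to half. Neither the 30% nor the share has a source in the documents, and a shift the other way would favor the intervention. The point bears mainly on the one-year heroin comparison and leaves the figure of 219 per arm untouched.

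**What to change.** 1. Ask one sign-based overdose question, worded identically in both arms at baseline and at 3, 6 and 12 months: after opioid use, could not be woken, turned blue, or stopped or nearly stopped breathing. Count a self-reported event only if at least one sign is present, and record which.
2. Record naloxone receipt and emergency care separately. Naloxone receipt alone should not qualify an event: study kits go to one arm only, so using it as a criterion would bring back a difference between arms. The schedule already collects naloxone given to the subject.
3. Pre-specify a sensitivity analysis of Aim 1 restricted to overdoses confirmed by ED or hospital, ambulance or death records. State with it that 911 training in one arm may shift ambulance and ED capture.

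If the interview form already contains such an item, cite it in the protocol and add only the third step.

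The cost is interview wording and one further analysis; the training itself is unchanged. There are three downsides: controls hear a little overdose information, the event rate may fall slightly in both arms, and some signs depend on a bystander's account, which may itself be better informed in the intervention arm. The wording must be settled before the interviews, since the threshold cannot be restored afterwards.
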